STIs: sexually transmitted infections.

RESEARCHERS

[name] [name] [name] Dra. [name] Dra. [name]

INTRODUCTION

23.3 million people living with HIV/AIDS (PLWHA) are now receiving antiretroviral therapy (ART) and it is estimated that there will be 2.8 million more per year in the next 3 years (19). For continued access to ART and monitoring of clinical and virological progress, PLWHA must be maintained in high-quality care. **Retention in HIV care is associated with increased survival, viral suppression; and reduced HIV transmission and viral resistance** (20,21). Missing more than two HIV care visits increased mortality risk in a multicenter cohort study (HR = 3.61; 95% CI, 2.35-5.55) (21). Low retention in HIV care is a critical barrier to achieving optimal individual and community outcomes. Continuum of HIV care includes testing for exclusion, linkage to care, initiation of ART, retention, and adherence to therapy to achieve and maintain viral suppression. Since 2010, the number of new HIV infections in Latin America has remained stable, without significant decreases as observed in all other regions of the world (19). Viral suppression remains low in some regions: 22% in the Middle East and North Africa; 40% in the Caribbean; and 52% in Latin America (19). With the expansion of ART, urgent efforts are needed to retain PLWHA in care and thus reduce morbidity, mortality, and the incidence of new HIV-related infections (22-24).

HIV disproportionately affects men who have sex with men (MSM). MSM represent 41% of new infections in the region (19). In fact, MSM have a 27-fold higher risk of HIV infection than the general population (25). In Peru, the epidemic is concentrated among them (prevalence 12.2%), while only 0.4% of the general population is HIV+ (19,26). The incidence among MSM aged 18 to 29 years has increased substantially and 60% of new infections occur in this group (27,28). Of concern, HIV-positive MSM are less likely to remain in care than other population groups (29-33). In the United States, 54.3% retention in HIV care and 50.8% viral suppression were reported among MSM aged 20-24 years (32). In Peru, less than 50% of MSM have been tested for HIV and it is estimated that only 24% of those infected know their status (28). The Ministry of Health reported that retention in HIV care after the first year is 55%, which drops significantly during the second year (26). National viral suppression is only 36% (26).

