Finally, to specify possible mechanisms of action to promote a behavior, such techniques and functions must be connected to influences on behavior following this model. The proposed mechanisms of action to facilitate adherence behavior in WelTel were: a) the delivery of an external trigger (SMS reminder to complete a behavior) and social support, to influence opportunities and automatic motivation through restructuring and environmental clearance; b) delivery of health-related information and social support to influence ability, opportunity, and motivation through education, persuasion, and training. We believe that retention in HIV care will be similarly influenced in our intervention.

General description:

This intervention will be designed for MSM who are HIV positive. We will recruit subjects 18 years of age or older. The intervention will begin one day after enrollment. The two-way SMS intervention will have four components: 1) an automated weekly SMS sent to ask how they are doing (basic follow-up); 2) phone calls from a health provider to participants who respond that they have a problem, or that they need support or some information that cannot be resolved by text message; 3) SMS reminder 1 week before an appointment for HIV care.

Design:

Randomized controlled trial.

Main result:

The primary outcome will be retention in HIV care for up to 1 year after enrollment. Participants will be classified as retained in care if they attend three HIV care appointments that are separated by 90 days or more within a one-year period (at the study HIV center) (64). Otherwise, they will be classified as not retained. The delivery of the intervention will last 6 months and the follow-up period to verify retention will last up to 12 months.

Main exposure:

Text message (SMS) based intervention delivered through the WelTel system by trained health providers.

Procedures:

- 1. **Recruitment and eligibility criteria**. We will identify and recruit 208 HIV+ MSM in the Cayetano Heredia Hospital HIV service for a period of up to 12 months. Eligible participants will be 1) men who have sex with men; 2) 18 years or older; 3) has been diagnosed HIV positive; 4) own a cell phone that can send and receive SMS; 5) resides in Lima; and 6) not be enrolled in another study that uses text messaging.

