- 2. Enrollment and randomization: During enrollment, the recruiter will be blinded to assignment to the intervention group. The recruiter will obtain informed consent and instruct the participant on how he should interact if he starts receiving text messages (see appendix 1). Participants will be randomly assigned after providing their cell phone number and brief general information (first name, date of diagnosis, email). They will be assigned a study ID and randomly divided into intervention or control arm (1:1 ratio) using computer generated random numbers. Arm assignments will be in sequentially numbered sealed envelopes. Healthcare providers trained to administer the intervention will be informed by the research team when a new participant is enrolled in the intervention arm. Due to the nature of the study, healthcare providers and participants will not be blinded to group assignment. The participants assigned to the intervention arm will have their telephone numbers registered on the platform.
- 3. Intervention. We will use the WelTel platform. For 6 months, every Monday the system will send automatic SMS with the question "How are you?" or similar questions (How are you?; How are you doing?). Participants will be instructed to respond if they are okay ("All OK") or if they have a problem ("I want support"; "I'm not okay"). The provider will send a return SMS to participants who have a problem or query; or they will call those who need it. The WelTel program has a customizable dictionary that identifies the words (or phrases) that the administrator indicates; thus, the answers of the participants are automatically ordered to indicate who needs follow-up through a reply SMS or call. One week before each appointment for HIV care, health providers will send an SMS reminder (Table 1).

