- 4. Standard care arm. In 2018, the government published new national guidelines for HIV care (65). After pre-test counseling, the diagnosis of HIV is made with two rapid tests. Those who test positive for both tests receive post-test counselling, including emotional support, and are linked to an ART initiation center, ideally within the same week. During the first medical appointment after diagnosis, laboratory tests including CD4 and viral load (VL) are requested. In most cases, initiation of antiretroviral treatment (ART) occurs at the second medical appointment when basic laboratory results are available. Currently, it is not mandatory to have CD4/CV results available to start ART. ART, viral load and CD4

lab tests are provided free of charge. It is recommended that patients have CD4 counts and viral load testing twice during the first year. A one-month supply of ART is initially provided. If patients are adherent, nurses dispense ART every 3 months and also assess adherence.

Table 1. Summary of the study: exposures, results and design.

Component	Sub-	Description						
	component							
	Basic follow-up	Weekly automatic SMS with the question "How are you?" or similar						
	SMS (check-in)	messages. This will be shipped for 6 months.						
Intervention	Calls	The provider can call participants who have a problem.						
arm	Appointment	SMS reminder one week before each appointment for HIV care.						
(exposure)	reminders							
	Primary	Retention in HIV care up to 1 year after enrollment, defined as attending 3						
Results		appointments that are 90 days apart within a 1-year period.						
	Desing	Randomized controlled trial with a parallel group.						
		We aim to increase retention in HIV care from 50% to 70%. With 104						
	Sample size	participants in each arm, we will have 80% power to detect this difference						
Design	Follow-up	6 months (intervention); 12 months (retention measure).						
	Theory	The behavior change wheel framework and its model of Capability,						
		Opportunity, Motivation and Behavior.						
	Standard of care	Post-test counselling, including emotional support and linkage to ART						
Control arm		initiation, ideally within a week. ART, CD4, and viral load laboratory tests are						
		provided free of charge in Peru.						

Analysis plan:

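### Time since diagnosis is a likely prognostic factor, known before allocation, but the plan neither stratifies on it nor pre-specifies adjustment for it

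*Combined protocol and SAP*

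**What the plan says.** **Eligibility** (Methods, Procedures 1). The criterion on HIV status is "3) has been diagnosed HIV positive". None of the six criteria limits time since diagnosis, ART status or time in care. Recruitment is at one hospital HIV service.

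**Usual care** (Procedures 4 and the control row of Table 1). The text mostly follows a man entering care. Table 1 opens with "Post-test counselling, including emotional support and linkage to ART" initiation. Procedures 4 adds "During the first medical appointment after diagnosis, laboratory tests including CD4 and viral load (VL) are requested" and "It is recommended that patients have CD4 counts and viral load testing twice during the first year". One sentence fits established patients as well: "If patients are adherent, nurses dispense ART every 3 months and also assess adherence".

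**Retention figures.** For the country, the Introduction reports that "retention in HIV care after the first year is 55%, which drops significantly during the second year". The end of the Introduction gives 50% at the study site, without saying how long those patients had been diagnosed. The sample size section plans on 50% versus 70%.

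**Allocation** (Procedures 2). "Participants will be randomly assigned after providing their cell phone number and brief general information (first name, date of diagnosis, email"). Allocation is 1:1 from computer-generated random numbers in sealed envelopes. No strata or blocks are mentioned.

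**Analysis** (Analysis plan, statistical analysis). The arms are compared on the proportion retained. Mantel-Haenszel relative risks are calculated only if a variable of interest is unbalanced. Neither the variables nor a threshold for imbalance is given, and no analysis by time since diagnosis is planned.

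**The concern.** A man diagnosed last week and a man diagnosed years ago are both eligible. By the plan's own account retention changes with time in care, so the two may have different chances of meeting the outcome. The variable that separates them is in hand before the envelope is opened, and then goes unused.

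Two things follow. First, chance differences between arms in the mix of newer and established men add noise that could be removed at almost no cost. Second, adjustment depends on seeing an imbalance in a variable that nobody has named. The primary analysis would then be chosen after looking at the data, and two analysts could reasonably choose differently.

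There is also a gap in description. The reader is not told which patients the 50% refers to, nor, beyond a line or two, what usual care is for a man already established on treatment.

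**Working it through.** **1. The plan's sample size.** Inputs: 50% and 70%, 80% power, 104 per arm (sample size section). Alpha is not stated; I assume 0.05 two-sided.
- Without continuity correction: n = [1.960·√(2·0.6·0.4) + 0.842·√(0.25 + 0.21)]² / 0.20² = 93 per arm.
- With continuity correction: n = (93/4)·[1 + √(1 + 4/(93·0.20))]² = 103 per arm.

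The plan's 104 agrees with the corrected figure. Power at 104 per arm is 80.5% with the correction and 84.3% without.

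**2. Does pooling cost power?** The documents do not give the mix, so this is a range over assumptions. Take newer men at 50% control retention, established men at 40% to 80%, a newer share of 25% to 75%, and a 20-point effect in both groups. Continuity-corrected power at 104 per arm is then 79% to 96%. Pooling alone does no harm.

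Power falls only if the effect is smaller in established men. With half established at 50% control retention, it is 53.5% if their effect is 10 points (50% versus 65% overall) and 25.7% if it is nil (50% versus 60%). Nothing in the documents says that the effect is smaller.

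**3. What chance imbalance contributes.** Assume that a share s = 0.5 is established, with retention of 50% in newer and 80% in established men, the same in both arms.
- Overall retention: 0.5·0.50 + 0.5·0.80 = 0.65.
- Total variance per man: 0.65·0.35 = 0.2275. SE of the arm difference: √(2·0.2275/104) = 6.6 points.
- Within-group variance: 0.5·0.25 + 0.5·0.16 = 0.205. SE with the mix removed: √(2·0.205/104) = 6.3 points.
- Share due to the mix: (0.2275 − 0.205)/0.2275 = 9.9%.

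The same result as an imbalance: the SE of the difference in established share is √(2·0.25/104) = 6.9 points. Multiplied by the 0.30 gap, this moves the arm difference by more than 2.1 points in about 1 trial in 3, and by more than 4.1 points (1.96 SE) in about 1 in 20.

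**4. Sensitivity to the assumed gap** (half established, same formulas).
- 50% versus 70%: 0.01/0.24 = 4.2% of the variance; SE 6.8 to 6.7 points.
- 50% versus 60%, or 50% versus 40%: 0.0025/0.2475 = 1.0% of the variance; SE essentially unchanged at 6.9 points.

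**5. What the strata could show alone.** With 52 per arm in a half-size stratum, continuity-corrected power for 50% versus 70% is 46.8%. For a 20-point difference in effect between two equal strata, taking 50% and 70% as the arm rates in the variance, SE = √(0.46/52 + 0.46/52) = 13.3 points and power is about 32%. Stratum results can describe; they cannot separate the two groups.

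**The case against.** The strongest reply is that the plan is already sound on the main question. The stated target is broad: "This intervention will be designed for MSM who are HIV positive". The outcome clock runs from enrollment, not from diagnosis. Randomisation makes the comparison valid for whoever is enrolled, and chance imbalance is already counted in the ordinary standard error, so it is noise and not bias. The plan does provide for Mantel-Haenszel adjustment, and since date of diagnosis is collected (Table 2 lists it), retention by time since diagnosis can be tabulated whatever the allocation method. All of this stands. It limits the point to a modest precision gain and a fixed analysis in place of a triggered one.

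A reader might infer more, and the documents do not support it:
- *That control retention will exceed 50% because 50% describes first-year men.* Only the national 55% carries a first-year label. The site's 50%, which matches the planning value, carries none and may already reflect a mixed clientele.
- *That established men do better.* The documents give no such figure. The second-year drop could mean further loss among men still in care, or only a cumulative count. The direction is open.
- *That the control description does not fit established men.* Three-monthly dispensing with adherence assessment, and free ART and laboratory tests, apply to them too.
- *That the result could not be assigned to any population.* It applies to HIV-positive MSM at the service, which is what the objective asks.

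The objection does not rescue the adjustment rule. An imbalance trigger with no named variable and no threshold is not a specified analysis, and a prognostic variable is worth adjusting for whether or not it happens to be unbalanced.

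**Conclusion.** The point holds as an inexpensive improvement to design and analysis. It is not a flaw that invalidates the trial, and it calls for no change in sample size.

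Three statements are firm, because they rest on the text alone: eligibility is open on time since diagnosis, the plan itself links retention to time in care, and a variable known before allocation is used neither to stratify nor in a pre-specified adjustment. The size of the gain is not firm. It is about 10% of the variance (SE 6.6 to 6.3 points) if half the men are established and the gap is 50% versus 80%, about 4% at a 20-point gap, and about 1% at a 10-point gap. The documents give neither the mix nor the gap. The gain that needs no assumption is that the primary analysis would be fixed in advance.

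**What to change.** - Keep the eligibility criteria as they are.
- In Procedures 2, randomise from two envelope series: diagnosed 12 months or less before enrollment, and more than 12 months. Use permuted blocks of varying size within each; without blocks, separate series would not balance the arms. The 12-month cut is a convenient choice suggested by the first-year and second-year wording in the Introduction. The plan sets no such boundary.
- In the Analysis plan, make the Mantel-Haenszel relative risk over these two strata the pre-specified primary comparison, in place of the imbalance-triggered one.
- Report retention by arm within each stratum, labelled descriptive, with no claim of a difference in effect between strata.
- State which patients the site's 50% describes, and reconcile the usual-care text in Procedures 4 and Table 1 with the eligibility criteria.

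The cost is a second envelope series and a few sentences. No new data, visits, staff or participants are needed. The downside is the extra handling of two series, and stratum results that will be imprecise.

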 Data sources for the main result. The main outcome to be measured will be retention in HIV care during the first year after enrollment. Retention in care will be considered if they attend 3 HIV care appointments that are at least 90 days apart within a one-year period (64). We will verify retention in HIV care with: study registration (enrollment) sheets, physical medical records from the HIV service, reception appointment notebooks, and with a final follow-up survey.

Health providers will enter the data from the enrollment registration sheets into a database that will be stored in a password-protected computer file. The data from the final follow-up online survey completed by the participants will be exported to the physical database and will be periodically deleted from the online survey system server. All data resulting from the interaction between providers and participants will be stored on the WelTel platform that has high security standards: encrypted, password protected and HIPAA compliant (*The Health Insurance Portability and Accountability Act*).

Statistic analysis. for the main outcome, we will compare the proportion of MSM who
were retained in care in both groups, as a cumulative incidence rate. If any variable of
interest is not balanced between intervention and control arms, we will calculate Mantel

Haenszel-adjusted relative risks (RR). For secondary outcomes, we will also assess differences in the proportion of participants.

3. **Calculation of the sample size**. We hope to increase retention in HIV care from 50% to 70% one year after enrollment in the study clinic among HIV+ MSM. With 104 participants in each arm, we will have 80% power to detect this difference.

Our main outcome is the degree of loss to follow-up. Retention in care at the study HIV service (as opposed to being lost to follow-up) is the primary outcome, and retention in any HIV clinic will be a secondary measure. Participants lost to follow-up will be considered as not retained. We will measure the retention in an establishment of the Ministry of Health (MINSA). MINSA provides care to more than 60% of Peruvians (73). Since retaining subjects in our public health system is an important goal, we have not adjusted the sample size calculation based on the potential loss of subjects to follow-up.

OPERATIONALIZATION OF VARIABLES

Table 2. Operationalization of variables.

Variable	Туре	Options	Source				
Age	Continuous	> 18	Online follow-up survey				

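### Nobody is masked when retention is classified, and one listed outcome source (the WelTel system) appears to exist in the intervention arm only

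*Combined protocol and SAP*

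**What the plan says.** Procedures, item 2 (Enrollment and randomization) contains every statement on blinding. For recruitment: "During enrollment, the recruiter will be blinded to assignment to the intervention group". Assignments are in sequentially numbered sealed envelopes. After that the trial is open: "Due to the nature of the study, healthcare providers and participants will not be blinded to group assignment". Trained providers "will be informed by the research team when a new participant is enrolled in the intervention arm", so the research team also holds assignments. The same item says that men in the intervention arm have their phone numbers registered on the WelTel platform, and says nothing of the kind for control men.

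The primary outcome (Methods, Main result) requires three attended HIV care visits at the study center, spaced by at least 90 days, inside one year. Any man who does not meet this is not retained.

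The Analysis plan's paragraph on data sources verifies this from enrollment sheets, "physical medical records from the HIV service, reception appointment notebooks, and with a final follow-up survey". Participants complete that survey online. In Table 2, the retention row lists four sources: clinic history, appointment record, online survey and the WelTel system. No section says who reads these sources, whether that person or the analyst is masked, or which source prevails when they disagree.

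**The concern.** Masking the recruiter is sound allocation concealment, but it ends at enrollment. The outcome is determined up to a year later from several sources that may conflict, by an unnamed person who may know the arm.

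Two features give that knowledge room to act:

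- **Judgement at the margin.** The plan does not define an HIV care appointment. The description of standard care includes both medical appointments and nurse ART dispensing every 3 months with an adherence assessment, and does not say whether a dispensing contact counts. With three visits required, one contact counted or not can change a man's status.
- **Sources that differ by arm.** A WelTel record would reveal the arm and appears to offer additional evidence of attendance for intervention men only. The survey is self-report by men who know their arm.

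At stake is a difference in retention that comes partly from how records were read. Delivery cannot be blinded in this trial, but classification from records can be.

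**Working it through.** **1. The plan's own figure.** Inputs from the sample-size paragraph: 50% versus 70% retained, 104 per arm, 80% power. Alpha and sidedness are not stated; I assume 5% two-sided. Pooled-variance formula, with mean proportion 0.60:

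n = (1.960 + 0.842)² × 2 × 0.60 × 0.40 / 0.20² = 94.19

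With continuity correction:

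n = (94.19/4) × [1 + √(1 + 4/(94.19 × 0.20))]² = 103.95, which rounds up to 104.

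The stated size reproduces, so the sample size is not at issue.

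**2. Who knows the arm at classification.**

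| Role | Blinded? | Where |
|---|---|---|
| Recruiter | Yes, stated only for enrollment | Procedures, item 2 |
| Providers, participants | No | Procedures, item 2 |
| Research team | Passes intervention assignments to providers | Procedures, item 2 |
| Person classifying retention | Not stated | – |
| Analyst | Not stated | – |

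**3. Which sources carry the arm.**

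| Source | Listed in | Link to arm |
|---|---|---|
| Clinic history, appointment record | Analysis plan and Table 2 | None described |
| Final survey | Analysis plan and Table 2 | Completed by unblinded men |
| WelTel system | Table 2 only | Registration described for the intervention arm only |
| Enrollment sheets | Analysis plan, but not the Table 2 retention row | Table 2 credits them with email and phone number only |

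**4. How far apart the arms must be.** Suppose control has 52/104 retained. With 67/104 in the intervention arm, the pooled proportion is 119/208 = 0.572 and z = (15/104) / √(2 × 0.572 × 0.428/104) = 2.10. With 66/104, z = 1.959, just short of 1.960. So the smallest significant gap is 15 men. Subtracting 1/104 from the difference for continuity gives z = 1.962 at 67, so the threshold is the same. Five men upgraded in one arm would supply 5/15, a third of that gap.

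**5. Effect on type I error.** Assumptions: true retention is 50% in both arms, 104 per arm, and a fraction b of intervention men is moved from not retained to retained, with none moved in control. The observed proportions are then 0.50 and 0.50 + b. I summed the two binomial distributions over all outcomes in which the two-sided pooled z-test rejects at 5%.

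| b | Men (b × 104) | Share of truly non-retained men upgraded (b/0.50) | Exact, uncorrected | Exact, continuity-corrected |
|---|---|---|---|---|
| 0 | 0 | 0% | 4.5% | 3.2% |
| 2% | 2.1 | 4% | 5.4% | 3.9% |
| 4% | 4.2 | 8% | 8.2% | 6.2% |
| 6% | 6.2 | 12% | 13.1% | 10.4% |
| 8% | 8.3 | 16% | 20.2% | 16.6% |

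A normal approximation to the uncorrected test gives slightly more: 6.0%, 8.9%, 13.9% and 21.1% for b = 2% to 8%. The plan names no test, so both exact columns are shown.

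**The case against.** The strongest reply is that little is left to discretion. Table 2 records attended appointment dates as a date variable from the clinic history and appointment record. The rule is numerical, and both failure to meet it and loss to follow-up default to not retained. This stands, and it confines the exposure to borderline men: conflicting sources, and contacts that may or may not count as a visit.

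The size is also hypothetical. No document supports 2% to 8%, and upgrading 8% of the arm means misclassifying 16% of its truly non-retained men while misclassifying none in control. At 2% the error stays at about 5% or below. That also stands.

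Three stronger readings are tempting, and the documents do not support them:

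- **That the classifier is unblinded.** The plan is silent. It permits classification with the arm known but does not say that this happens.
- **That providers can shift the outcome through data entry.** The plan does say "Health providers will enter the data from the enrollment registration sheets into a database", and the Analysis plan names those sheets among the outcome sources. But Table 2 credits them only with email and phone number, and nothing shows that they hold follow-up visits.
- **That intervention men have fuller charts that invite a closer search.** Provider–participant exchanges are stored on the WelTel platform. No section says that they enter the charts or notebooks, or that the WelTel providers write those charts.

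Nor is the recruiter's blinding at fault. It does what it is meant to do.

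**Conclusion.** The concern holds as an omission with a practical remedy. The plan masks nobody at outcome classification, and it lists one source that appears to exist in one arm only and another that is self-report by unblinded men. The possible bias is confined to borderline cases.

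Its size cannot be established from the documents. Under the stated assumptions (no true effect, 50% retention, 104 per arm, one-sided upgrading of 2% to 8% of intervention men), type I error runs from about 5% to 20% with an uncorrected test and from about 4% to 17% with continuity correction. At the low end there is no material inflation. A reader might infer from the upper figures that the trial's error rate is already several times nominal. They show only what a given amount of one-sided reading would do.

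The statement about WelTel rests on the plan describing platform registration for the intervention arm alone. It does not say what the system would contribute to the retention variable.

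**What to change.** Amend the Analysis plan's data-source paragraph and the retention row of Table 2 as follows.

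1. Determine primary retention in both arms from the same sources: the clinic history and the appointment record.
2. Leave WelTel data and self-report out of the primary classification. Self-report may inform the secondary measure of retention in any HIV clinic.
3. Have attended-visit dates and visit types abstracted from a list of study IDs without the arm, by an existing team member who did not deliver WelTel and has no access to the allocation list or the WelTel roster. The recruiter should not be assumed to qualify, because the plan states that blinding only for enrollment.
4. Compute retained or not by a fixed program that applies the plan's stated rule to those dates.
5. Merge the arm only after the dates are locked.

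The sample size stays at 104 per arm. The cost is protocol wording, an ID list without the arm column, and keeping the roster apart from the abstraction file. The plan does not show that a team member without access to assignments is available, so the sponsor should confirm this. A chart note that mentions the messages may occasionally reveal the arm.

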WelTel was the first randomized controlled trial using an interactive two-way text messaging approach that reported a significant increase in adherence and viral suppression in Kenya (RR for non-adherence: 0.81, 95% CI: 0.69 -0.94; RR for virologic failure 0.84, 95% CI: 0.71-0.99), as well as among HIV+ women in Vancouver, BC (38,46). WelTel is based on a well-structured platform that connects healthcare providers with patients through regular text messages. It uses a web-based program (software) (accessed through the Internet) with intuitive functionalities that allow providers to monitor, track and support large numbers of people (47). The platform allows addressing multiple morbidities, as well as different health services. The system has been tested in Kenya, Rwanda, South Africa, the United States, and Canada and has been used for other diseases such as tuberculosis and asthma (46,48,49). A recent study with WelTel in Kenya significantly improved Quality of Life scores ("the 4th 90") (40). HIV+ MSM in Peru may benefit from receiving an SMS-based intervention delivered through the WelTel platform to increase low retention in HIV care (retention = 50% at study site).

JUSTIFICATION

Peru is a relevant place to test an SMS intervention to increase retention in HIV care based on existing WelTel technology. The country has a high number of cell phone subscriptions (121 per 100 people), and smartphone use is also very common and constantly growing (50-52). Our preliminary data shows that Peruvian MSM are interested in receiving HIV prevention information via SMS (2,3,50,53). Other studies report that HIV+ MSM are interested in interacting with health providers to discuss HIV-related issues that may positively affect their retention in care (55). The proposed study will develop, implement, and evaluate an adapted version of WelTel to deliver a two-way interactive SMS intervention to increase retention among HIV+ MSM. WelTel has been used extensively in other resource-limited settings, and there is preliminary information in Peru to help tailor the content of such an intervention (3,4,12,40,43,49,55).

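### Does the primary outcome need a rule on whether the enrollment-day visit is one of the three qualifying visits?

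*Combined protocol and SAP*

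**What the plan says.** The visit rule appears four times: under Methods (Main result), in Table 1, in the Analysis plan (Data sources for the main result) and in Table 2. The Analysis plan wording is "Retention in care will be considered if they attend 3 HIV care appointments that are at least 90 days apart within a one-year period". None of the four mentions a care visit on the enrollment day.

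The window is given next to the rule. The Methods say "The primary outcome will be retention in HIV care for up to 1 year after enrollment". The Analysis plan, in the sentence before the rule, says "The main outcome to be measured will be retention in HIV care during the first year after enrollment". Methods and Table 2 restrict the appointments to the study's own HIV center.

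On timing, the Methods say "The intervention will begin one day after enrollment" and "The delivery of the intervention will last 6 months and the follow-up period to verify retention will last up to 12 months". Table 1 repeats this as "6 months (intervention); 12 months (retention measure)".

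The sample size section adds "Participants lost to follow-up will be considered as not retained". The Introduction supplies the planning rate: "low retention in HIV care (retention = 50% at study site)".

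**The concern.** Recruitment takes place in the HIV service, so enrollment can fall on the day of a care visit. If that visit counts, two later visits complete the outcome. If it does not, three are needed. The same attendance dates could then be coded either way.

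The timing sharpens the point. Visits on days 0, 90 and 180 would satisfy a one-year retention outcome while messages are still being sent. A benefit that fades after month 6 might then show under one convention and not under the other. A man seen on days 0, 91 and 182 and never again would be retained by the visit rule with day 0 counted, yet might be called lost to follow-up. The 50% planning rate would also belong to an unnamed convention. If the convention were picked after seeing attendance by arm, the type I error rate would no longer be protected.

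**Working it through.** **1. The plan's own figure.** Inputs from the sample size section: 50% against 70%, 104 per arm, 80% power. The documents give no significance level, so two-sided 5% is assumed.

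- Uncorrected: n = [1.960·√(2·0.6·0.4) + 0.842·√(0.5·0.5 + 0.7·0.3)]² / 0.2² = (1.358 + 0.571)² / 0.04 = 93.0.
- With continuity correction: (93/4)·[1 + √(1 + 4/(93·0.2))]² = 102.8, so 103 per arm, against 104 stated.
- Power at 104 per arm: 80.5% corrected, 84.3% uncorrected.

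The stated size reproduces.

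**2. Timing.** Messages start on day 1. Six calendar months are 181 to 184 days, so they end on day 182 to 185. If the first qualifying visit is on day f, the earliest third is on day f + 180.

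- Day 0 counted: 0 + 180 = 180, which leaves 2 to 5 days of slack across two intervals. Intervals of 92 days give 184. Intervals of 93 days give 186, already past the latest end date.
- Day 0 not counted: a first later visit on day 30 gives 210, and on day 91 gives 271.

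So counting day 0 lets the outcome finish within the message period only if visits are almost exactly 90 to 92 days apart.

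**3. Attendance patterns.** Four scheduled follow-up visits give 2⁴ = 16 attended/missed patterns. A pattern is retained if it holds three visits at least 90 days apart within days 0 to 365. The schedules are assumptions: the three-month interval in the Standard care arm section concerns ART dispensing.

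| Visit days | Retained, day 0 not counted | Retained, day 0 counted | Change class | Earliest completion with day 0 |
|---|---|---|---|---|
| 90, 180, 270, 360 | 5 | 11 | 6 | day 180 |
| 91, 182, 273, 364 | 5 | 11 | 6 | day 182 |
| 30, 120, 210, 300 | 5 | 8 | 3 | day 210 |

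In the first row, the six that change are the men attending exactly two follow-up visits: 90+180, 90+270, 90+360, 180+270, 180+360 and 270+360. Five of these include a visit after day 185. Only 90+180 is retained with nothing after the messages end. In the third row nobody completes by day 185 under either convention. The same is true for visits on days 95, 190 and 285, where the earliest completion with day 0 is day 190.

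**4. Power if the planning rates belong to the other convention.** Two assumed models are used: independent visits with equal probability, or men who leave at a constant quarterly rate and do not return. Power is Φ{[d − 1/n − 1.960·√(2p̄(1−p̄)/n)] / √([p₁(1−p₁) + p₂(1−p₂)]/n)}, with n = 104.

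| 50%/70% refers to | Analysis | Model | Rates | Power |
|---|---|---|---|---|
| later visits only | counts day 0 | independent | 83.7%/93.6% | 53% |
| later visits only | counts day 0 | leave for good | 63.0%/78.8% | 66% |
| day 0 counted | later visits only | independent | 16.3%/32.5% | 73% |
| day 0 counted | later visits only | leave for good | 35.4%/58.6% | 90% |

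In the leave-for-good rows, 0.50^(2/3) = 0.630 and 0.50^(3/2) = 0.354, and likewise for 0.70. Power moves in both directions, and nothing in the documents selects a row.

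**5. Error rate.** With no effect and one convention fixed, each test rejects in about 4.5 to 5.2% of trials. Taking whichever convention is significant raises this to 6.4, 7.5, 8.2 and 8.8% when 5, 10, 20 and 33.7% of men change class. The excess comes from choosing late, which the plan does not propose.

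**The case for a change.** The strongest reply is that the text does not fully close the question. Enrollment sheets head the list of sources for verifying retention, which an analyst could take as support for counting that day. Providers and participants are unblinded, and no blinded classification of the outcome is described, so a late choice is possible. With a true 50%/70% effect, the two conventions disagree on p < 0.05 in 12 to 33% of trials across the four settings above. Even a man who misses nothing can be affected: on an assumed schedule of days 88, 176, 264 and 352 he has two qualifying visits without day 0 and three with it (0, 176, 352).

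It stands that the convention is unwritten and that it can change the class of some men. The rest is weaker. Enrollment sheets are needed under either convention, because they date the start of the year. The Procedures describe enrollment as consent, instruction and registration by a recruiter and never call it a care appointment. The disagreement rates rest on invented attendance models, and two correlated binary outcomes will often fall on opposite sides of a threshold.

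The conflict over loss to follow-up is also narrower than it seems. The sample size section uses that phrase as the opposite of being retained, so a man who meets the visit rule can be read as not lost. The question is in any case separate from day 0: a man seen on days 30, 120 and 210 and never again raises it too.

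**Conclusion.** No change to the plan follows. The omission is real, but it is a missing detail that an analyst can fill from the adjacent text: study-center care appointments dated after enrollment and within 12 months. Randomisation makes the comparison fair under either convention, provided the same one is used in both arms, and the attended dates listed in Table 2 support either coding without new data. No stated rule or number is shown to be wrong, and the 104 per arm reproduces.

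The alarming consequence, an outcome completed while messages still run, needs day 0 to count and visits to be spaced almost exactly 90 to 92 days apart. On exact quarterly visits it makes a man retained with no later attendance in one of 16 patterns; on the two other schedules tried (days 30, 120, 210, 300 and days 95, 190, 285), in none. The power range of 53% to 90% and the 6 to 9% false-positive range are illustrations. They depend on assumed attendance models, an assumed two-sided 5% level and, for the false positives, a late choice of convention. The number of men affected cannot be found from the documents; if there are none, the two conventions coincide.
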